APPENDIX 4. DERIVATION OF CDAI SCORES

a. Definition of CDAI Score

The CDAI score is comprised of 8 items ([Table 16](#)). The total CDAI score is the sum of each item times the multiplier. If any of the subscores are missing, then the CDAI score is set to missing.

Table 16: CDAI Score

Item Description	Multiplier
Number of liquid or soft stools (each day for 7 days)	× 2
Abdominal pain, sum of 7 daily ratings (0=none, 1=mild, 2 = moderate, 3=severe)	× 5
General well-being, sum of 7 daily rating (0=generally well, 1=slightly under par, 2=poor, 3=very poor, 4=terrible)	× 7
Number of listed complications (arthritis or arthralgia, iritis or uveitis, erythema nodosum or pyoderma gangrenosum or aphthous stomatitis, anal fissure or fistula or abscess, other fistula, fever over 37.8°C [100°F])	× 20
Use of diphenoxylate or loperamide for diarrhea (0=no, 1=yes)	× 30
Abdominal mass (0=no, 2=questionable, 5=definite)	× 10
Hematocrit (males, 47-HCT [%], females, 42-HCT [%])	× 6
Body weight (1-weight/standard weight) x 100 ^a	× 1

^a if the calculated body weight item score is less than -10, set to -10

HCT = Hematocrit

b. Data Sources for the Derivation of Each CDAI Item

- Daily number of liquid or soft stools; daily abdominal pain; daily general well-being, use of diarrhea medications: Clario e-diary
- Endoscopy date: Alimentiv data
- Bowl preparation date: Clario data, if the recorded endoscopy date in Clario data matches the date in the Alimnetiv source data
 - In case of discrepancy, the day prior to endoscopy date will be assumed to be bowl preparation date
- Listed complications; abdominal mass: Clario data
- Hematocrit: Laboratory data (note: for Week 14 CDAI, hematocrit values from baseline of trial 20038 may be used, if applicable)
- Body weight: CRF data (note: for Week 14 CDAI, weight values from baseline of trial 20038 may be used, if applicable)
- Standard weight: standard height-weight table (see [Table 17](#))
- Height: CRF

c. Window for Patient-Reported Outcomes

In general, the patient-reported outcomes of stool frequency, abdominal pain, general well-being, and use of diarrhea medications are based the e-diary data collected in a 7-day window prior to the assessment of CDAI, which may be extended to 10 days. The evaluable days for the e-diary data do not include the day of bowel preparation, the day of endoscopy, and the 2 days after endoscopy. A minimum of 3 consecutive days with completed diary entries or 4 nonconsecutive days are necessary to calculate the CDAI stool frequency, abdominal pain, and general well-being items, otherwise the score will be considered missing.

Details regarding the window for patient-reported outcomes will be provided in a separate CDAI derivation rules document that will be finalized prior to DBL.

d. Special Rules for Derivation of CDAI Score at Screening, Baseline, Weeks 2-12, and Week 14

Specific derivation rules of CDAI Score at Screening, Baseline, Weeks 2-12, and Week 14 will be provided in a separate CDAI derivation rules document that will be finalized prior to DBL.

e. Standard Height and Weight

Table 17: Standard Height and Weight Table

Actual Height cm (inches)	Standard Weight in kg Men (Pounds)	Standard Weight in kg Women (Pounds)
147.3 (58.0)		52.2 (115.0)
148.6 (58.5)		52.6 (116.0)
149.9 (59.0)		53.1 (117.0)
151.1 (59.5)		53.6 (118.3)
152.4 (60.0)		54.2 (119.5)
153.7 (60.5)		54.8 (120.8)
154.9 (61.0)		55.3 (122.0)
156.2 (61.5)		56.0 (123.5)
157.5 (62.0)	61.7 (136.0)	56.7 (125.0)
158.8 (62.5)	62.1 (137.0)	57.4 (126.5)
160.0 (63.0)	62.6 (138.0)	58.0 (128.0)
161.3 (63.5)	63.0 (139.0)	58.7 (129.5)
162.6 (64.0)	63.5 (140.0)	59.4 (131.0)
163.8 (64.5)	64.1 (141.3)	60.1 (132.5)
165.1 (65.0)	64.6 (142.5)	60.8 (134.0)
166.4 (65.5)	65.2 (143.8)	61.4 (135.5)
167.6 (66.0)	65.8 (145.0)	62.1 (137.0)
168.9 (66.5)	66.4 (146.5)	62.8 (138.5)

Table 17: Standard Height and Weight Table (Continued)

Actual Height cm (inches)	Standard Weight in kg Men (Pounds)	Standard Weight in kg Women (Pounds)
170.2 (67.0)	67.1 (148.0)	63.5 (140.0)
171.5 (67.5)	67.8 (149.5)	64.2 (141.5)
172.7 (68.0)	68.5 (151.0)	64.9 (143.0)
174.0 (68.5)	69.2 (152.5)	65.5 (144.5)
175.3 (69.0)	69.8 (154.0)	66.2 (146.0)
176.5 (69.5)	70.5 (155.5)	66.9 (147.5)
177.8 (70.0)	71.2 (157.0)	67.6 (149.0)
179.1 (70.5)	71.9 (158.5)	68.3 (150.5)
180.3 (71.0)	72.6 (160.0)	68.9 (152.0)
181.6 (71.5)	73.4 (161.8)	69.6 (153.5)
182.9 (72.0)	74.1 (163.5)	70.3 (155.0)
184.2 (72.5)	75.0 (165.3)	
185.4 (73.0)	75.7 (167.0)	*Height in shoes with one-inch heels
186.7 (73.5)	76.6 (169.0)	
188.0 (74.0)	77.5 (171.0)	*Indoor clothing weighing 5 pounds for men and 3 pounds for women
189.2 (74.5)	78.4 (172.8)	
190.5 (75.0)	79.1 (174.5)	
191.8 (75.5)	80.2 (176.8)	*Centimeters x 0.3937 = inches
193.0 (76.0)	81.2 (179.0)	*Pounds x 0.4536 = kilograms

APPENDIX 5. PRO2-CD SCORE

Table 18: Definition of PRO2-CD Score

Score	Data	Derivation
PRO2-CD Stool Frequency Subscore	Mean number of liquid or soft stools in 7-day period	Mean value <0.5 → subscore=0; Mean value ≥ 0.5 and < 1.5 → subscore =1; Mean value ≥ 1.5 and < 2.5 → subscore = 2; Mean value ≥ 2.5 → subscore =3
PRO2-CD Abdominal Pain Subscore	Mean abdominal pain in 7-day period	
PRO2-CD Score	Sum of stool frequency and abdominal pain subscores	

Derivation of PRO2-CD Score:

- Calculate the stool frequency and abdominal pain mean values at: derived baseline, weeks 2 to 12, and week 14 using the rules as described in [Appendix 4](#) for CDAI.
- Derive the subscores (range 0-3) as described in [Table 18](#).
- PRO2-CD is the sum of the stool frequency and abdominal pain subscores.

Note that the binary efficacy endpoints based on PRO2-CD (see [Table 5](#)) use cutoffs for the mean values and not the subscores.

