	
 Clinical remission defined as score of rectal bleeding = 0 and stool frequency = 0 on the PRO2-UC scale at week 14 
The secondary efficacy endpoints to be measured in participants with moderate to severe CD are as follows:
 
 Clinical response defined as a ≥ 100-point decrease in Crohn's Disease Activity Index (CDAI) score from baseline at weeks 4, 8, 12 and 14 Clinical remission defined as a CDAI score < 150 at week 14 Clinical response defined as a decrease from baseline of at least 50% in PRO2 (PRO2-CD; abdominal pain and stool frequency) at week 14 Clinical remission defined as abdominal pain ≤ 1 and stool frequency ≤ 3 on the PRO2 scale at week 14 Endoscopic response defined as a decrease in modified multiplier (MM)-SES-CD of $> 50\%$ from baseline at week 14

A secondary objective of the trial is to evaluate the safety and tolerability of 3 different dose regimens of TEV-48574 sc administered Q2W in adult participants with IBD (moderate to severe UC or CD).
	
The safety and tolerability measures/parameters are as follows:
 
 Adverse events Change from baseline in clinical laboratory test results (serum chemistry, hematology, and urinalysis) Change from baseline in vital signs measurements (blood pressure, pulse rate, body temperature, and respiratory rate) Change from baseline in 12-lead electrocardiogram findings Participants who stopped the investigational medicinal product due to adverse events Local tolerability at the injection site

A secondary objective of the trial is to evaluate the immunogenicity of 3 different dose regimens of TEV-48574 sc administered Q2W in adult participants with IBD (moderate to severe UC or CD).
	
The immunogenicity endpoints for this trial are as follows:
 
 Treatment-emergent anti-drug antibody (ADA) at weeks 2, 4, 8, 14, and follow-up visit

Objectives	Endpoints
	
• Presence of neutralizing ADA in ADA positive participants at weeks 2, 4, 8, 14, and follow-up visit

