4.3.2. Missing items – MMS, CDAI, PRO2-UC, and PRO2-CD

The MMS, CDAI, PRO2-UC and PRO2-CD are composite scores (see derivation rules in [Appendix 4](#), [Appendix 5](#)). The patient-reported items of stool frequency (UC and CD), rectal bleeding (UC), and abdominal pain (CD) are based on e-diary data collected in a 7-day window before the assessment date of the score, which may be extended to 10 days prior to the assessment date, as described in [Appendix 4](#). A minimum of 3 consecutive days of completed diary entries or 4 nonconsecutive days are necessary for each parameter, otherwise the corresponding item will be considered missing.

If any item of a composite score is missing, then the score will be considered missing.

If a score is missing, then the participant will be considered a non-responder /non-remitter for all binary outcomes based on this score, except for intermittent missing data visits that will be excluded from that visit analyses.

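### The PRO2-CD total score cannot register stool-frequency gains that stay at or above 2.5 stools/day, and the SAP does not settle which scale the 50% and 30% PRO2-CD responses use

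*SAP*

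**What the plan says.** Three parts of the SAP bear on this.

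- **The score.** Appendix 5, Table 18 places mean values in bands cut at 0.5, 1.5 and 2.5. The top band is "Mean value ≥ 2.5 → subscore =3". The instructions below the table read "Derive the subscores (range 0-3) as described in" (Table 18), and then "PRO2-CD is the sum of the stool frequency and abdominal pain subscores". Section 4.3.2 treats PRO2-CD as a composite score and refers to Appendices 4 and 5 for its derivation. No other PRO2-CD total appears in the SAP.
- **The endpoints.** Section 1.1 lists a secondary response, "Clinical response defined as a decrease from baseline of at least 50% in PRO2 (PRO2-CD; abdominal pain and stool frequency) at week 14", and a secondary remission, "Clinical remission defined as abdominal pain ≤ 1 and stool frequency ≤ 3 on the PRO2 scale at week 14". Section 1.3 and Table 5 add exploratory remissions with stool-frequency limits of 2.8 and 1.5, and an exploratory response at a 30% decrease. The PRO2-CD total score is itself exploratory at seven visits (Section 1.3). Section 6.4 summarises and graphs it as change from baseline, and Section 5.4 lists PRO2-CD as a baseline characteristic.
- **The note.** Appendix 5 closes by saying that the binary PRO2-CD endpoints in Table 5 "use cutoffs for the mean values and not the subscores". Table 5 contains both the remissions and the percent-decrease responses.

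**The concern.** Bands at 0.5, 1.5 and 2.5 fit a pain rating that runs from 0 to 3. A daily stool count has no such upper limit, so 2.6 and 8 stools/day both score 3. The SAP's own remission limits of 3 and 2.8 stools/day therefore reach into the worst stool category of its own score.

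Two things follow. The total score is not a binary endpoint, so the closing note does not reach it and the ceiling applies on any reading. For the responses, the note points to means, but a percent decrease in PRO2 needs a total and the only total is the banded sum. Programmers working independently could reach different responder counts for a named secondary endpoint, which Section 6.3.1.1 analyses by four methods. If the scale is chosen after unblinding, the responder definition becomes a post hoc choice.

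**Working it through.** **Inputs.** Bands and sum: Appendix 5, Table 18. Remission limits (pain at most 1, stool frequency at most 3 or 2.8, on means): Sections 1.1 and 1.3, Table 5, closing note. Weights 2 (stools) and 5 (pain): Table 16, used only as one candidate formula. The bands are taken to apply to both items, which agrees with the stated 0-3 range. Participant profiles are illustrative, because the SAP gives no distribution of stool counts or pain.

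**The plan's own range.** Applying the bands to any mean returns only 0, 1, 2 or 3. The stated range is reproduced, and the total runs from 0 to 6.

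**Ceiling on the total score.** Stools falling from 8 to 2.6/day: subscore 3 before, 3 after, change 0.

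**One participant, three scales.** Baseline 6 stools/day, pain 2.0; week 14, 2.8 stools/day, pain 0.6. Remission is met at both the 3 and the 2.8 limit.

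| Scale | Baseline | Week 14 | Decrease | 50% response |
|---|---|---|---|---|
| Sum of subscores | 3 + 2 = 5 | 3 + 1 = 4 | 1 − 4/5 = 20% | no (also fails 30%) |
| Sum of means | 6 + 2.0 = 8.0 | 2.8 + 0.6 = 3.4 | 1 − 3.4/8.0 = 57.5% | yes |
| 2 × stools + 5 × pain | 12 + 10 = 22 | 5.6 + 3.0 = 8.6 | 1 − 8.6/22 = 61% | yes |

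Using 7-day sums in place of daily means multiplies both weighted totals by 7 and leaves the percentage unchanged.

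**General limit on the subscore scale.** If week-14 stools are 2.5/day or more, the final total is at least 3. The largest baseline is 6, so a 50% decrease requires baseline 6 and a final pain subscore of 0, meaning pain falls from at least 2.5 to below 0.5. A remitter with week-14 stools of 2.5-3 and pain of 0.5-1 has a final total of 4. The largest possible decrease is then 1 − 4/6 = 33.3%, so none can be a 50% responder.

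**Following the note literally still leaves a choice of formula.**

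| Profile (stools/pain) | Subscores | Sum of means | Weighted 2 and 5 |
|---|---|---|---|
| 6/1 to 2.5/1 | 4 to 4, 0% | 7 to 3.5, 50% | 17 to 10, 41% |
| 4/2.5 to 3/0.5 | 6 to 4, 33% | 6.5 to 3.5, 46% | 20.5 to 8.5, 59% |

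In the first row only the sum of means gives a 50% responder; in the second, only the weighted score does.

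**What a mean-based score does not remove.** 4/2 to 3/1 meets remission with a decrease of 1 − 4/6 = 33.3% unweighted, or 1 − 11/18 = 38.9% weighted. 5/2 to 3/1 gives 1 − 4/7 = 42.9%, or 1 − 11/20 = 45%.

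**The case against.** The strongest reply is that the closing note settles the matter. It names the Table 5 binary endpoints, the responses are among them, and it rules out subscores, so the 2.5 ceiling would play no part in response. As a literal reading this is fair, and it means that a reader who infers that the secondary response *will* be scored on capped subscores goes further than the text. But the note speaks of cutoffs. That suits the remission limits, and is needed there, since every participant would satisfy a stool limit of 3 on a 0-3 subscore. A percent decrease has no item cutoff and needs a total, which the note does not supply. The separate derivation document promised in Appendix 4 is described only for diary windows and CDAI rules.

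Four further objections stand, at least in part.

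- A reader might infer that remission without response is created by the ceiling. It is not. Remission is an absolute threshold and response a relative change, so they can disagree at low baselines on any scale. On the subscore scale, the ceiling makes disagreement possible at higher baselines too.
- A reader might infer that treatment effects are diluted, or that the score hardly sees stool frequency at all. Neither is shown. Falls below 2.5/day do register (6 to 1 stools/day scores 3 to 1), and the SAP gives no data on how many participants would be reclassified.
- Nothing in the SAP says PRO2-CD is weighted. The Table 16 multipliers belong to the CDAI and are only one option.
- The CD primary endpoint is SES-CD, the total score is exploratory, and Section 7 makes no multiplicity adjustment, so no success decision depends on this.

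**Conclusion.** The point holds in two parts. First, on any reading the PRO2-CD total score cannot register stool-frequency improvement that stays at or above 2.5/day, a range that includes the plan's remission limits of 2.8 and 3. Second, the SAP conflicts with itself on the scale for the 50% and 30% responses, and the choice can reverse an individual's responder status: 20% against 57.5% or 61% in the main example.

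This rests on the bands applying to both items and on illustrative profiles. The effect on responder counts or treatment differences cannot be computed from the document. Only secondary and exploratory CD endpoints are affected. It is a should-fix, to be settled before database lock and unblinding.

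**What to change.** In Appendix 5:

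1. Define the PRO2-CD score used for the 50% and 30% responses and for the total score from unbanded mean daily values, with one stated formula. Twice the mean stools plus five times the mean pain, in line with the Table 16 multipliers, is one option; an unweighted sum is another. The formula must be named because the two can disagree.
2. Drop the 0-3 banding for stool count.
3. Reword the closing note so that response and remission explicitly use the same mean values.

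Some remission without response will remain at low baselines, and the study report can say so. The cost is a paragraph in the appendix and a change to derivation code. No new data are needed.

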APPENDIX 6. CORTICOSTERIODS - EQUIVALENT PREDNISONE DOSE

The equivalent prednisone dose for different oral corticosteroids, is provided in [Table 19](#).

Table 19: Equivalent Prednisone Dose

Corticosteroid	Equivalent Dose (mg)
Cortisone	25
Hydrocortisone	20
Prednisone	5
Prednisolone	5
Triamcinolone	4.0
Methylprednisolone	4.0
